### 8. PROTOCOL VERSION 3.0 ANALYSIS IMPACT

Protocol version 3.0, dated June 8, 2022, made significant changes to the study design including adding a 2nd dose of study drug and two interim analyses. These changes are reflected in the SAP.

Due to this protocol version occurring during the study, some participants will receive only a single injection at baseline and complete the study at day 180 instead of day 270 as per the protocol prior to v3.0 if they did not sign informed consent for v3.0. In effect they will not complete the study under protocol v3.0 and will be considered pre-3.0 participants. These participants will be included in the ITT and Safety populations (if applicable) but will be excluded from the PP population.

Summary tables of the ITT and Safety populations will combine pre-3.0 and post-3.0 participants. Informed consent, disposition, and randomization tables and listings will delineate those who were considered pre-3.0 and those who were post-3.0.

### XALUD THERAPEUTICS, INC. Study Drug: XT-150

●	
•	
• • • • • • • • • • • • • • • • • • •	
•	
	•

### **10. STATISTICAL ANALYSES**

### **10.1.** Informed Consent and Randomization

Informed consent, reconsent, enrolled or consented into protocol v3.0 prior to day 90, and randomization information will be summarized and listed by participant for the All Participants population.

### **10.2.** Analysis Populations

Using the Randomized Population, the number and percent of participants in the ITT, Safety, will be provided.

### **10.3.** Screened Participants

Using the All Participants population, the number of screened participants will be summarized as well as the number and percentage of participants who were enrolled and randomized and reasons for non-enrollment and not being randomized.

Inclusion/exclusion criteria that were failed for screen failures will be summarized at baseline and screening separately. Inclusion/exclusion findings will be listed, with screening and baseline screen failures listed separately.

### **10.4.** Participant Disposition

Participant disposition will be summarized for the Randomized population. Due to this study only having a single dose of treatment at Day 0 and 90, no disposition related to treatment discontinuation is needed in this section as those reasons will be captured in the treatment administration section. Instead, due to protocol v3.0 and the addition of a 2nd dose at day 90, there are four "pathways" that a participant can take in the study and will be summarized from the Day 90 study administration form. Summaries will include:

- Total number of participants who withdrew from study and reason for withdrawal.
- Number of participants who passed day 90 prior to protocol v3.0 reconsent.
  - Number of participants who completed at day 180.
  - Number of participants who discontinued prematurely and reasons for discontinuation.
- Number of participants who were enrolled into protocol v3.0.
  - Number of participants who received the 2nd dose at day 90.
  - Number of participants who completed at day 270.
  - Number of participants who discontinued prematurely and reasons for discontinuation.
- Number of participants who reconsented to protocol v3.0 prior to day 90 to receive a 2nd dose at day 90.

- Number of participants who received the 2nd dose at day 90.
- Number of participants who completed at day 270.
- Number of participants who discontinued prematurely and reasons for discontinuation.
- Number of participants who reconsented to protocol v3.0 prior to day 90 but did not consent to receive a 2nd dose at day 90.
  - Number of participants who completed at day 180.
  - Number of participants who discontinued prematurely and reasons for discontinuation.

A study flow diagram will be produced showing the total number of subjects screened, randomized, treated at day 0 and day 90, and the overall "pathway" of the study including reasons for discontinuation.

Participant disposition data will also be presented in listings.

### **10.5. Protocol Deviations**

In accordance with International Council for Harmonisation (ICH) E3, Sponsor-defined eligibility violations and important (major versus minor) protocol deviations will be identified and summarized by type of deviation in the ITT population.

All protocol deviations will also be listed by participant and including the type of deviation.

### **10.6.** Demographics and Baseline Characteristics

Demographic and baseline characteristics will be listed and summarized descriptively for the ITT and Safety populations. The following demographic and baseline data will be summarized: sex, age, race, ethnicity, height, weight, BMI,

. Age is provided in the  $\overline{\text{EDC}}$  at date of informed consent.

A demographic listing will also be provided.

Screening and on-study pregnancy serum/urine test results will also be listed.

### **10.7.** Medical and Surgical History

Medical and Surgical history collected at screening will be coded using Medical Dictionary for Regulatory Activities (MedDRA), version 24.1. Medical and Surgical history will be summarized for the Safety Population by system organ class and preferred term.

Medical and Surgical history will be listed, with FJOA related history highlighted.

### 10.7.1. FJOA Related Medical History

Medical and surgical history related to FJOA collected at screening will be coded using Medical Dictionary for Regulatory Activities (MedDRA), version 24.1. FJOA related medical and surgical history will be summarized for the Safety population by system organ class and preferred term.

### **10.8. Prior and Concomitant Medications**

Verbatim terms on case report forms will be mapped to Anatomical/Therapeutic/Chemical (ATC) class and generic drug name using the World Health Organization (WHO) drug dictionary, WHO Drug – Global B3, September 2021.

Prior medications are those medications started before the start of study drug. Concomitant medications are those medications taken after the start of study drug. As such, prior medications continued after the use of study drug are also considered concomitant medications. Prior and concomitant medications will be summarized for the Safety population by ATC class (level 3) and preferred term. Participants receiving the same medication more than once are counted only once for each ATC class and preferred term.

In addition, separate summaries including only back pain medication will be provided using the same format.

Prior and concomitant medications will be listed by participant, and a separate listing with medications taken for back pain will also be provided.

### **10.9.** Study Drug Treatment Administration

Participants will receive a single dose of XT-150 (or placebo) consisting of two injections bilaterally into the facet joint at baseline and another at Day 90. The following information will be summarized for the Randomized population at each visit:

- Site of injections (L3-L4, L4-L5, L5-S1).
- Number of participants receiving any XT-150 or placebo.
- Reasons participants did not receive any XT-150 or placebo.
- Number of participants receiving the full dose of XT-150 or placebo (both injections) at each timepoint individually.
- Reasons that the full dose was not administered.
- Number of participants receiving the full dose at both timepoints.

Treatment administrations will be listed, with information about each bilateral injection listed separately.

### 10.10. Confirmation of FJOA and Lidocaine Facet Selection

Confirmation of FJOA by imaging and lidocaine facet selection will be performed at screening. The following information will be summarized in the Safety population: number of participants with FJOA confirmation by scan type, number of lidocaine tests performed to select target facet joint, and the selected facet joint location for treatment.

FJOA imaging and lidocaine facet selection details will be listed.

### 10.11. Assessment of IL-10 Antibodies and IL-10 Protein

IL-10 protein and anti-IL-10 antibodies results will be summarized for the Safety population across study visits.

IL-10 related information will be listed for each participant.

#### **10.12.** Plasma DNA Biodistribution

Sample collection and presence of plasmid DNA in whole blood will be summarized across study visits for the Safety population.

Plasmid DNA related information will be listed for each participant.

#### **10.13.** Efficacy Analysis

[figure not shown]
All efficacy analyses will be conducted on the ITT Population as randomized.

#### 10.13.1. VAS Pain Indicator Chart Score

#### 10.13.1.1. Primary Efficacy Analysis

The VAS Pain indicator chart is a score from 0-100 with 100 being the worst score and is collected at each study visit.

The VAS Pain score will be summarized at each visit, including change from baseline at each visit.

All VAS pain scores will be listed for each participant by visit.

### XALUD THERAPEUTICS, INC. Study Drug: XT-150

If $\geq$ 7 participants receive only a single dose as per the pre

[figure not shown]

#### 10.13.2. Oswestry Disability Index (ODI)

The Oswestry Disability Index (ODI) is a 10-category index where each score is given an ordinal integer between 0-5, where 5 is the worst score. The Oswestry disability score is a composite 0%-100% disability score that will be summarized based on the composite of the individual scores as (Total score from individual components / (# of questions completed \* 5)) x 100. Typically, this will be (Total Score / 50) x 100 if a participant completes the entire questionnaire.

Oswestry Disability individual raw scores and the Oswestry disability score (%) will be listed for each participant by visit.

#### 10.13.3. Participant Global Assessment

The participant global assessment is a score from 1-5, where 5 is the worst score. The score will be summarized at each visit, including shifts from baseline for each score and descriptive statistics with changes from baseline.

Participant global assessment scores will be listed for each participant by visit.

#### **10.13.4.** International Physical Activity Questionnaire (IPAQ)

The IPAQ is a questionnaire with multiple categories that will be summarized across study visits. The following measures will be summarized as continuous by randomization arm (sub-bullets use reduced N based on how many answer the previous question as >0):

- During the last 7 days, how many did you do vigorous physical activities? (0-7 days)
  - How much time did you spend per day doing vigorous physical activities on those days? (hours)
- During the last 7 days, how many did you do moderate physical activities? (0-7 days)
  - How much time did you spend per day doing moderate physical activities on those days? (hours)
- During the last 7 days, how many did you walk at least 10 minutes at a time? (0-7 days)
  - How much time did you spend walking on those days? (hours)
- During the last 7 days, how much time did you spend sitting on a weekday? (hours)

### IPAO values will be listed for each participant by visit.

[figure not shown]
#### **10.13.5. Quality of Life (SF-12v2)**

The SF-12v2 questionnaire has multiple sections with multiple-choice questions based on physical and mental quality of life. The answers to the SF-12v2 questionnaire will be scored through QualityMetric PRO CoRE standard software as standardized scores or "T scores". With

T scores, scoring is standardized across the Short Form adult surveys using the means and SDs from the 2009 U.S. general population, with a mean of 50 and SD of 10.

Missing data estimation methods of "Maximum Data Recovery" from the PRO CoRE software will be used in generation of the T scores. This method allows the software to use partial information to make calculations of scores for respondents who have answered only a part of the multi-item scales. This allows the Physical Component Summary (PCS) and Mental Component Summary (MCS) to be calculated with at least 7 of the 8 categories completed. However, PCS will not be calculated if the Physical Functioning (PF) scale is missing and MCS is not calculated if the Mental Health (MH) scale is missing. These T scores will be categorized into the following scales:

- Physical Component Summary (PCS): All scores contribute; physical-related scores are more heavily weighted. T score range: 4.62 76.36.
- Mental Component Summary (MCS): All scores contribute; mental-related scores are more heavily weighted. T score range: 1.32 79.48.
- Physical Functioning (PF): Items 2a, 2b. T score range: 22.1 56.47.
- Role-Physical (RP): Items 3a, 3b. T score range: 20.32 57.18.
- Bodily Pain (BP): Item 5. T score range: 16.68 57.44.
- General Health (GH): Item 1. T score range: 18.87 61.99
- Vitality (VT): Item 6b. T score range: 27.62 67.88.
- Social Functioning (SF): Item 7. T score range: 16.18 56.57.
- Role-Emotional (RE): Items 4a, 4b. T score range: 11.35 56.08.
- Mental Health (MH): Items 6a, 6c. T score range: 15.77 64.54.

SF-12 T scores categories will be listed for each participant by visit.

### 10.14. Safety Analyses

All safety analyses will be conducted on the safety population. Participants will be summarized by treatment arm, visit (where applicable), and time (where applicable). For all safety analyses, in cases where participants received the wrong study medication, participants will be summarized based on the treatment received.

#### 10.14.1. Adverse Events

AEs will be coded to system organ class (SOC) and preferred term according to MedDRA, version 24.1. Pretreatment AEs are defined as AEs that have an onset on or after the date the informed consent was signed but before the date of the first dose of study drug. Treatment-emergent adverse events (TEAEs) are defined as AEs that start or worsen after the first dose of study drug. Adverse event severity will be graded using CTCAE v5.0.

Summaries will be provided for TEAEs, with the number and percentage of participants reporting each type of event presented. If a participant reports the same preferred term more than once, it is counted only once within that category. Similarly, if a participant has AEs of two or more preferred terms under the same SOC, then that participant only counts once for that SOC. Furthermore, for a given summary, the preferred term will only be counted once at its worst severity and strongest relationship to study drug.

AEs of special interest will be identified programmatically and reviewed by the study team prior to unblinding. AEs of special interest include:

- (Unexplained) fever
- Grade 2+ allergic, cytokine release, or infusion-related reactions Therapy or infusion interruption indicated but responds promptly to either:
  - symptomatic treatment (e.g., antihistamines, NSAIDS, narcotics, IV fluids)
  - prophylactic medications indicated for  $\leq$ 24 hours
- Grade 2+ injection site reactions
- Grade 2+ neutropenia

The following summaries and listings for AEs will be provided:

- An overall summary table of AEs summarizing the number and percent of participants, in the following categories: any AE, any TEAE, TEAEs by highest severity grade, any TEAEs of special interest, TEAEs by relationship to study drug (related, not related), any serious TEAE, TEAEs leading to drug withdrawal, and TEAEs leading to premature withdrawal from the study, any TEAEs with a fatal outcome
- Incidence of TEAEs by MedDRA SOC and preferred terms
- Incidence of TEAEs by MedDRA SOC, preferred terms, and maximum severity grade
- Incidence of TEAEs by MedDRA SOC, preferred terms, and relationship to study drug.

- Incidence of TEAES of special interest, by SOC, preferred terms, and maximum severity grade.
- Incidence of SAEs by SOC, preferred terms, and maximum severity grade
- Listing of all AEs (with non-treatment-emergent events flagged and AEs of special interest highlighted).
- Listing of all AEs of special interest
- Listing of AEs leading to drug withdrawal
- Listing of all SAEs

In addition, all deaths will be listed with the primary cause of death and whether an AE is associated with the death.

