## 9.4. Day 90 (±7 days)

- Clinical Assessments:
  - Brief physical exam, including the injection site for infections or inflammation
  - Measure vital signs (temperature, heart rate, blood pressure, and respiratory rate)
- Efficacy assessments
  - VAS score
  - Oswestry Disability Index
  - IPAQ short form
  - SF12
  - Record participant's response to the question: "Considering all the ways that
    Facet pain, the pain that brought you into this study, affects you, how are you
    doing today?" on a scale of 1 to 5, 1 being very good (asymptomatic and no
    limitation of normal activities) to 5, very poor (very severe, intolerable symptoms
    and inability to carry out normal activities)
  - Record changes in drug regimens or pain therapy
- Assess, identify, and record any AEs since last visit
- Record any changes in concomitant medications since including prescription, OTC, and herbal medications.
- Laboratory assessments
  - Obtain urine pregnancy test and evaluate results. Participant must have negative urine pregnancy test prior to dosing.
  - Obtain serum for analysis of IL-10 protein and anti-IL-10 antibodies
- Administer study drug (see Section 8 for details on preparation)
  - Aseptic techniques will be used in the preparation and administration of XT-150
  - Injections will be guided by ultrasound, fluoroscopy or equivalent visualization
  - All injections of study drug must be performed by a specialist who is qualified, trained, and experienced to perform intra-articular injections to the Facet joint.
  - Examine injection site for infections or reactions
- Clinical assessments post-study drug administration
  - Monitor Participant for approximately for 1 hour for signs of study drug reaction
  - Measure vital signs (temperature, heart rate, blood pressure, and respiratory rate) at least once about 1 hour after injection

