## 10.7.2. Localized Signs of Infection or Inflammation at the Injection Site

Events that, in the opinion of the Investigator, may represent localized signs of infection or inflammation at the XT-150 injection site (e.g., pain, erythema, swelling, pruritus, warmth, hematoma, induration) must be recorded as AEs on the CRF. In general, these events will be temporally related to the injection.

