### 4. STUDY OBJECTIVES AND ENDPOINTS

### 4.1. Study Objectives

#### Primary objectives:

• To evaluate the safety and tolerability of a repeat bilateral intra-articular dose of XT-150.

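### Repeat-dose safety is the primary objective, but no visible adverse-event table shows incidence after the second dose or recurrence on re-dosing

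*SAP*

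**What the plan says.** SAP 4.1 gives the primary objective: "To evaluate the safety and tolerability of a repeat bilateral intra-articular dose of XT-150". Protocol 5.1.1 agrees. Doses are planned at Day 0 and Day 90 (SAP Section 3).

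SAP 10.14.1 anchors treatment emergence to the first injection: "Treatment-emergent adverse events (TEAEs) are defined as AEs that start or worsen after the first dose of study drug". It then sets the counting rules. First: "If a participant reports the same preferred term more than once, it is counted only once within that category". Second, within a given summary, "the preferred term will only be counted once at its worst severity and strongest relationship to study drug". The incidence outputs it lists are an overall table, tables by system organ class and preferred term (alone, by maximum severity, by relationship), a special-interest table and an SAE table. None mentions dose period or second-dose recipients. Protocol 14.4 adds no such split.

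SAP Section 8 says: "Summary tables of the ITT and Safety populations will combine pre-3.0 and post-3.0 participants". The two groups are separated only in consent, disposition and randomization outputs. The number of single-dose participants is not given.

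Other safety output bears on the second dose:
- At Day 90, Protocol 9.4 asks staff to "Examine injection site for infections or reactions" and "Monitor Participant for approximately for 1 hour for signs of study drug reaction", with vital signs about an hour after injection.
- Under Protocol 10.7.2, suspected local infection or inflammation at the injection site "must be recorded as AEs on the CRF".
- SAP 10.14.3 and 10.14.4 summarize injection-site findings and vital signs by visit. SAP 7.1.2 and 10.14 allow a further split by time point where applicable.
- SAP 10.9 counts who received any dose and the full dose at each dosing visit, with reasons where not.
- AEs are listed, and SAP 7.2 sorts safety listings by treatment received and then participant.

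**The concern.** A participant who has an event after dose 1 only, after dose 2 only, or after both contributes the same single count to a preferred-term row. So the planned AE tables cannot answer two plain questions about re-dosing: how often events occurred after the second injection among those who had it, and whether people who reacted once reacted again. This holds even if every participant is re-dosed. Pooling one-dose participants adds to it by an unknown amount.

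The AE tables matter more here than usual. SAP Section 11 drops change-from-baseline laboratory summaries, because no laboratory tests are scheduled after screening. It also drops the physical-examination summary, because abnormal findings are to be captured as AEs. A local reaction that begins and ends between visits reaches a summary only through the AE tables. If the visible plan is followed, the second-dose figures must be rebuilt from listings or added later, and SAP 7.2 would label anything added after database lock as post-hoc and exploratory.

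**Working it through.** **Inputs.** There are 24 participants per arm (SAP 5.2; Protocol 14.1). Visit windows are Day 90 ±7, 120 ±7, 210 ±7 and 270 ±14 (Protocol Table 1; SAP Table 4). Event counts and the number re-dosed are assumed, because the documents give neither. Intervals are exact (Clopper-Pearson), two-sided 95%.

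**The plan's own figure.** Protocol 14.1 gives about 29% to 71% around a 50% rate. Exact limits for 12/24 are 29.1% to 70.9%, so the arm size and method reproduce. It is the only precision figure in the documents, and none is given for AE rates.

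**What one displayed cell can mean, all 24 re-dosed.** Suppose a preferred-term row shows 6/24 (25.0%). Let a = after dose 1 only, b = after dose 2 only, c = after both, with a + b + c = 6.
- Incidence after dose 2 is (b + c)/24. It runs from 0/24 (CI 0 to 14.2%) to 6/24 = 25.0% (CI 9.8% to 46.7%).
- The number with recurrence, c, runs from 0 to 6.
- There are C(8,2) = 28 such splits. Any cumulative table has this property, so 28 illustrates the ambiguity and does not measure a defect.

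**The same cell with 17 of 24 re-dosed (assumed).**
- Six react after dose 1 and the same six react again: 6/17 = 35.3% after dose 2 (CI 14.2% to 61.7%).
- Six react after dose 1 and none after dose 2: 0/17 (upper limit 19.5%).
- Both display as 6/24.

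**Effect of the denominator alone.** With k single-dose participants and a 25% event rate after dose 2 among those re-dosed, dividing by all 24 shows 0.25 × (24 − k)/24:

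| k (assumed) | Rate shown over 24 |
|---|---|
| 0 | 25.0% |
| 3 | 21.9% |
| 6 | 18.8% |
| 9 | 15.6% |
| 12 | 12.5% |

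**What the by-visit rows already cover.**
- If all are re-dosed, every row from Day 120 on follows dose 2. That visit falls 113 − 97 = 16 to 127 − 83 = 44 days after the second injection.
- If some are not re-dosed, the Day 120 to 180 rows are mixed. The Day 210 to 270 rows are then almost entirely two-dose participants, because SAP 7.3 uses available-data denominators and single-dose participants finish at Day 180. It is almost, because a final Day 180 visit held after Day 195 would fall into the Day 210 analysis window. The Day 210 visit is 203 − 97 = 106 to 217 − 83 = 134 days after dose 2.
- Day 90 has a site examination before dosing and another with the injection. SAP 7.5 keeps one assessment per window and the earlier on a tie. Read literally, the pre-dose examination fills that row unless a time point is shown.

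**Length of the two periods.** Dose 1 to dose 2 is nominally 90 days (83 to 97). Dose 2 to Day 270 is nominally 180 days, from 256 − 97 = 159 to 284 − 83 = 201. For those not re-dosed, the first period runs to Day 180.

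**Partial dates.** SAP 7.3 decides only whether an event is treatment-emergent. In its own example treatment starts on 12 March 2022. Day 90 is then 10 June (window 3 to 17 June), so an AE dated only June 2022 could belong to either period.

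**The case against.** The strongest reply is that nothing is contradicted. The endpoints in SAP 4.2 are not defined per dose, and the objective can fairly be read as the safety of the Day 0 plus Day 90 regimen, which cumulative tables by arm describe. Onset and dosing dates are collected and second-dose recipients are counted (SAP 10.4, 10.9). With at most 24 per arm, a listing sorted by participant puts repeat events side by side. In an unpowered Phase 2a trial, the added tables would be descriptive.

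Most of this stands. It means that the cumulative tables should stay and that nothing is irrecoverable. It does not close the gap: a listing is not an incidence summary, and even on the regimen reading the pooled tables include people who never received the regimen.

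Several stronger readings are not supported:
- That all the AE output is limited to events after the first dose. The overall table has a row for any AE, and the SAE table is not worded as treatment-emergent only. Neither separates the doses, however.
- That the by-visit tables say nothing about dose 2 until Day 210. That applies only if an appreciable number were not re-dosed.
- That monthly visits lose reactions. AEs are recorded at each visit for the time since the last one.
- That pooling seriously dilutes the rates. The number of single-dose participants is unknown.
- That no dose-period split exists anywhere. Parts of the SAP are redacted, including a contingency for seven or more single-dose participants. Its visible fragment sits in the VAS section, and the 10.14.1 output list appears intact, but a split elsewhere cannot be excluded.

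**Conclusion.** The point holds for the visible text. No AE incidence table in SAP 10.14.1 shows what happened after the second injection among those who received it, or whether an event recurred, although repeat dosing is the primary objective. The ambiguity is present with every participant re-dosed. In the assumed 6/24 row, incidence after dose 2 could be anywhere from 0% to 25.0%. The denominator effect is additional and of unknown size.

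A reader might go further and conclude that the trial cannot meet its primary objective, or that the cumulative tables are wrong. The documents do not support either. The tables are valid for treatment as given, the data needed are planned, and by-visit site findings, vital signs, dosing counts and listings cover part of the question. This is a gap in tabulation and worth closing because closing it is cheap.

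One separate, minor inconsistency should not add weight to this point. Protocol 14.4 ends AE collection, and 10.4.4.1 ends the death-reporting requirement, at Day 180. Protocol 5.2.1, 10.2 and Table 1 run safety or AE collection to Day 270. Read alone, the Day 180 wording would leave out 270 − 180 = 90 of the 180 nominal days after dose 2.

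**What to change.** **SAP 10.14.1.** Keep the cumulative tables. Add descriptive tables of TEAEs, serious TEAEs, AEs of special interest and injection-site-reaction AEs, by arm, for two periods:
1. first dose to before the second dose;
2. second dose onward, among participants who received it.

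Count each preferred term once per period, with participants dosed in that period as denominator. Show days at risk for each period. Add one row for re-dosed participants with the same preferred term in both periods.

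**SAP 7.3.** Add a rule that assigns an AE with a partial start date to a period.

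**Separately.** Reconcile the Day 180 wording in Protocol 14.4 and 10.4.4.1 with the Day 270 wording in 5.2.1, 10.2 and Table 1.

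**Cost.** A few extra tables from dates already collected, one date rule and one wording reconciliation. Made before database lock, this is an SAP amendment (SAP Section 2). Made later, it should carry the post-hoc label. The downsides are smaller denominators, a second period about twice as long as the first, and a second-period group formed after randomization. The tables are therefore descriptive only, and crude percentages should not be compared across periods. No sample-size or precision figure changes.
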